6.11.6 Exploratory Efficacy Analyses

AUC of WHO Ordinal Scale for Clinical Improvement will be summarized using descriptive statistics by treatment group.

6.11.7 Multiplicity

Holm (1979) step-down procedure will be used to control multiplicity for selected key secondary endpoints (days in ICU and days on mechanical ventilation).

If the primary analysis of the primary endpoint is significant at the <0.05 level key secondary endpoints days in ICU and days on mechanical ventilation will be tested using the Holm step-down procedure. In this way an overall type 1 (false-positive) error rate of 5% will be maintained so that no statistical significance for the key secondary efficacy endpoints will be claimed unless the principal analysis of the primary efficacy endpoint using the ITT set is statistically significant at the 5% level.

Holm procedure will be applied as follows:

1. If the p-value for primary endpoint ≥ 0.05 then testing will stop and key secondary endpoints will not be tested. If p-value <0.05 then testing continues to key secondary endpoints.
2. P-values for key secondary endpoints will be sorted from smallest to greatest (ascending order).
3. The smallest p-value for key secondary endpoints will be compared to 0.025.
4. If the smallest p-value yields significant result at 0.025 level then sequential testing continues to the next largest p-value and adjusted alpha value of 0.05. Otherwise the testing will stop.

Data from all analyses, regardless of the level of significance, will be presented for review.

Controlled Quality Management Document	
	Sponsor: Veru Inc.
	Protocol Number: V3011902
STATISTICAL ANALYSIS PLAN. PHASE 2-3-4	

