Secondary Objectives:	
The secondary objectives/endpoints on this study are:
 
 
1. The proportion of subjects that are alive without respiratory failure at Day 15, Day 22 and Day 29. Day 29 is the key secondary endpoint in this study. Respiratory failure is defined as endotracheal intubation and mechanical ventilation, extracorporeal membrane oxygenation, high-flow nasal cannula oxygen delivery, noninvasive positive pressure ventilation, clinical diagnosis of respiratory failure with initiation of none of these measures only when clinical decision making is driven solely by resource limitation.
 
2. Days in ICU
 
3. WHO Ordinal Scale for Clinical Improvement change from baseline to Day 15, Day 22, and Day 29
 
 
  
 Patient State	Descriptor	Score	
   
 Uninfected	No clinical or virological evidence of infection	0	
 
 Ambulatory	No limitation of activities	1	
 
 	Limitation of activities	2	
 
 Hospitalized, Mild disease	Hospitalized, no oxygen therapy	3	
 
 	Oxygen by mask or nasal prongs	4	
 
 Hospitalized, Severe disease	Non-invasive ventilation or high-flow oxygen	5	
 
 	Intubation and mechanical ventilation	6	
 
 	Ventilation + additional organ support – pressors, RRT, ECMO	7	
 
 Death	Death	8	
  
 
 
4. Days on mechanical ventilation
 
5. Days in hospital
 
6. Proportion of subjects that die on study at Day 15, Day 22, and Day 29.
 
7. Change from baseline in viral load (baseline to Day 9)
 
	Patient State	Descriptor	Score	Uninfected	No clinical or virological evidence of infection	0	Ambulatory	No limitation of activities	1		Limitation of activities	2	Hospitalized, Mild disease	Hospitalized, no oxygen therapy	3		Oxygen by mask or nasal prongs	4	Hospitalized, Severe disease	Non-invasive ventilation or high-flow oxygen	5		Intubation and mechanical ventilation	6		Ventilation + additional organ support – pressors, RRT, ECMO	7	Death	Death	8

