### 3.3 Study Rationale

In a Phase 2, double-blind, placebo-controlled clinical study the safety and efficacy of VERU-111 in the treatment of SARS-CoV-2 in patients at high risk for ARDS was assessed. Thirty-nine (39) hospitalized patients at high risk for ARDS were randomized to 18 mg of VERU-111 (powder in capsule formulation) or matching placebo. The primary efficacy endpoint for the study was the proportion of patients alive without respiratory failure at Day 15, Day 22, and Day 29. The key secondary endpoints in the study were days on mechanical ventilation, days in intensive care unit (ICU), and proportion of patients discharged from the hospital on Day 15, Day 22, and Day 29. The efficacy conclusions in the Intent-to-Treat (ITT) population from a post-hoc analysis from the Phase 2 study are:

- VERU-111 reduced the proportion of patients who died on study (up to Day 60) from 30% (6/20) in the placebo group to 5% (1/19) in the VERU-111 treated group. This is an approximately 82% reduction in mortality in the VERU-111 treated group.
- VERU-111 reduced the proportion of patients that are treatment failures, i.e. death or respiratory failure from 35.0% in the placebo group to 15.8% in the VERU-111 treated group at Day 15 and from 30.0% in the placebo group to 10.5% in the VERU-111 treated group at Day 29. This represents an approximately 55% reduction in treatment failures at Day 15 and a 65% reduction in treatment failures at Day 29 in the VERU-111 treated group compared to placebo.
- VERU-111 reduced the days on mechanical ventilation from an average of 5.4 days in the placebo group to 1.6 days in the VERU-111 treated group. This represents a 3.4-fold increase in the days on mechanical ventilation in the placebo group compared to the VERU-111 treated group.
- VERU-111 reduced the days in ICU from an average of 9.6 days in the placebo group to 3.0 days in the VERU-111 treated group. This represents a 3.2-fold increase in the days in the ICU in the placebo group compared to the VERU-111 treated group.
- There is an imbalance in the gender distribution between the treatment group such that the placebo group is 85% male (17/20) and the VERU-111 treated group is 53% male (10/19). This imbalance was evaluated as a covariate in the analysis but did not have a significant effect on the conclusions of the study.
- The use of remdesivir and dexamethasone did not have a significant effect on patient outcomes in the study.

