- In patients with a WHO disease severity score of  $\geq 5$  at baseline, the proportion of patients that died on study (up to Day 60) in the placebo group was 46% compared to 10% in the VERU-111 treated group. This represents a 78% reduction in death in the

VERU-111 treated group compared to placebo. It is important to note that in the Phase 2 study, the 6 patients in the placebo group and the 1 patient in the VERU-111 treated group that died on study all had a WHO disease severity score of  $\geq 5$  at baseline. Therefore, randomization into the Phase 3 study will be stratified by WHO scale at baseline such that patients who have a WHO disease severity score of 4, 5, and 6 at baseline are approximately equally distributed between the treatment groups. This is a similar population as was used in the Phase 2 study and accounts for patients that move from WHO severity score of 4 to 5 and then from WHO severity score of 5 to 6 to 7 quickly.

The Phase 2 clinical study was hypothesis generating. A 78-82% reduction in mortality, a 55-65% reduction in death or respiratory failure, 3.2-fold higher mean days in ICU and 3.4-fold higher mean days on mechanical ventilation in the Placebo group compared to the VERU-111 treated group are all clinically relevant observations and warrant the continued development of VERU-111 in the treatment of SARS-CoV-2 in patients at high risk for ARDS.

There were no drug related serious adverse events (SAEs) observed in the Phase 2 clinical study of VERU-111 in SARS-CoV-2 infected patients. There were no drug related serious adverse reactions ( $\geq$ Grade 3).

The relative bioavailability (pharmacokinetics) of the VERU-111 powder in capsule (PIC) formulation has been assessed and compared to a to-be-marketed VERU-111 formulated capsule (FC) formulation. Additionally, the effect of high fat meal (food effect) was also assessed for both formulations. The data are presented in Table 1.

**Table 1 The Steady State Pharmacokinetics of VERU-111 Powder in Capsule (PIC) and Formulated Capsule (FC) Under Fasted and Fed Conditions**

	63 mg PIC (fasted)	63 mg PIC (fed)	31.5 mg FC (fasted)	31.5 mg FC (fed)
N	6	6	6	6
Cmax (ng/mL)	148.1 $\pm$ 64.7	97.8 $\pm$ 53.5	182.2 $\pm$ 32.6	169.9 $\pm$ 104.2
Tmax (hr)	2.17 $\pm$ 0.98	7.67 $\pm$ 2.66	1.67 $\pm$ 1.21	4.08 $\pm$ 2.69
AUC 0-24h (ng $\cdot$ hr/mL)	1006.16 $\pm$ 376.29	984.80 $\pm$ 519.62	973.58 $\pm$ 307.87	1011.27 $\pm$ 512.54

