## 9.5 Secondary Endpoint

Primary analysis of secondary endpoints will be performed on the ITT analysis set and the ITT data scope regardless of patient's use of rescue medications, protocol violations or investigational product discontinuation consistent with the treatment policy strategy.

Full details for the handling of missing data, and consideration of subjects that die during the study for those endpoints that do not directly incorporate death, will be included in the Statistical Analysis Plan.

### 9.5.1 Proportion of patients alive and free of respiratory failure at Day 29, Day 15 and Day 22

Respiratory failure is defined as endotracheal intubation and mechanical ventilation, extracorporeal membrane oxygenation, high-flow nasal cannula oxygen delivery, noninvasive positive pressure ventilation, clinical diagnosis of respiratory failure with initiation of none of these measures only when clinical decision making is driven solely by resource limitation.

This analysis will compare the percentage of subjects that are alive without respiratory failure (responder) on Day 29 and on Day 15 and on Day 22.

Proportion of subjects alive and free of respiratory failure will be analyzed separately at each timepoint using the same logistic regression methodology as primary endpoint ([section 9.4.1](#)).

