3.2 Secondary Endpoints

The secondary endpoints on this study are:

1. The proportion of subjects that are alive without respiratory failure at Day 15, Day 22, and Day 29. Day 29 is the key secondary endpoint. Respiratory failure is defined as endotracheal intubation and mechanical ventilation, extracorporeal membrane oxygenation, high-flow nasal cannula oxygen delivery, noninvasive positive pressure ventilation, clinical diagnosis of respiratory failure with initiation of none of these measures only when clinical decision making is driven solely by resource limitation.
2. Days in ICU
3. WHO Ordinal Scale for Clinical Improvement change from baseline to Day 15, Day 22, and Day 29
4. Days on mechanical ventilation
5. Days in hospital
6. Proportion of subjects that die on study at Day 15, Day 22, and Day 29.
7. Change from baseline in viral load (baseline to Day 9)

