14.2.1.11	Proportion of Subjects Alive by Region, Country and Site, and Visit ITT Set	IP	14.2.1.1
14.2.1.12	Logistic Regression for Proportion of Subjects Alive by Region and Visit ITT Set	Stat IP	14.2.1.2
14.2.1.13	Proportion of Subjects Alive by Standard of Care and Visit ITT Set	IP	14.2.1.1
14.2.1.14	Logistic Regression for Proportion of Subjects Alive by Standard of Care and Visit ITT Set	Stat IP	14.2.1.2

	
	
	
	

Controlled Quality Management Document		
	Sponsor:	Veru Inc.
	Protocol Number:	V3011902

Table Number	Table Title	Validation Method	Shell Number (if repeat)
14.2.1.15	Proportion of Subjects Alive by WHO Ordinal Scale at BL and Visit ITT Set	IP	14.2.1.1
14.2.1.16	Logistic Regression for Proportion of Subjects Alive by WHO Ordinal Scale at BL and Visit ITT Set	Stat IP	14.2.1.2
14.2.1.17	Proportion of Subjects Alive by Vaccination Status (All Vaccinated (at Least One Shot) vs. All Unvaccinated) and Visit ITT Set	IP	14.2.1.1
14.2.1.18	Proportion of Subjects Alive by Vaccination Status (All Vaccinated with US Acceptable Vaccine vs. the Rest of the Population) and Visit ITT Set	IP	14.2.1.1
14.2.1.19	Proportion of Subjects Alive by Vaccination Status (All Vaccinated with at Least One Shot within 6 Months of the First Dose on V3011902 vs. the Rest of the Population) and Visit ITT Set	IP	14.2.1.1
14.2.2.1	Proportion of Subjects Alive and Free of Respiratory Failure by Visit ITT Set	IP	14.2.1.1
14.2.2.2	Logistic Regression for Proportion of Subjects Alive and Free of Respiratory Failure by Visit ITT Set	Stat IP	14.2.1.2
14.2.3.1	Descriptive Statistics for Days in Intensive Care Unit (ICU) - Death Assigned to Worst Possible Outcome ITT Set	IP	
14.2.3.2	Analysis of Covariance (ANCOVA) for Days in Intensive Care Unit (ICU) - Death Assigned to Worst Possible Outcome ITT Set	Stat IP	

Controlled Quality Management Document		
	Sponsor:	Veru Inc.
	Protocol Number:	V3011902

Table Number	Table Title	Validation Method	Shell Number (if repeat)
14.2.3.3	Descriptive Statistics for Days in Intensive Care Unit (ICU) by Region - Death Assigned to Worst Possible Outcome ITT Set	IP	14.2.3.1
14.2.3.4	Analysis of Covariance (ANCOVA) for Days in Intensive Care Unit (ICU) by Region - Death Assigned to Worst Possible Outcome ITT Set	Stat IP	14.2.3.2
14.2.3.5	Descriptive Statistics for Days in Intensive Care Unit (ICU) by Standard of Care - Death Assigned to Worst Possible Outcome ITT Set	IP	14.2.3.1

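### Alive without respiratory failure at Day 29 is declared the key secondary endpoint but has no place in the SAP 6.11.7 testing scheme, whose p<0.05 gate also conflicts with protocol 9.7.2

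*SAP*

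**What the plan says.** Protocol 2.0 states that "Day 29 is the key secondary endpoint in this study", meaning the proportion alive without respiratory failure. Protocol 4.2 and 5.3.2 and SAP 2.2 and 3.2 say the same; SAP 3.2 reads "Day 29 is the key secondary endpoint".

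SAP 6.11.7 uses the term differently: "Holm (1979) step-down procedure will be used to control multiplicity for selected key secondary endpoints (days in ICU and days on mechanical ventilation". The smaller of the two p-values is compared with 0.025 and, if that succeeds, the other with 0.05. The section states that an overall 5% false-positive rate is thereby maintained.

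Day 29 is analysed. Protocol 9.5.1 says "Proportion of subjects alive and free of respiratory failure will be analyzed separately at each timepoint", SAP 6.11.5.1 applies the primary-endpoint method, and Table 14.2.2.2 is titled "Logistic Regression for Proportion of Subjects Alive and Free of Respiratory Failure by Visit ITT Set". SAP 6.11 sets a default two-sided 5% level for all tests. No visible passage places Day 29 in the testing order or passes alpha to it. The visible text of SAP section 9 records that Holm was added, but no change of key secondary.

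The gate to the Holm pair is "If the primary analysis of the primary endpoint is significant at the <0.05 level". Protocol 9.7.2 sets the primary criterion at two-sided 0.0160 at the interim (about 150 of 210 subjects) and 0.0452 at the final analysis. SAP sections 7 and 8 refer interim analyses to a separate IDMC plan.

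**The concern.** A key secondary endpoint is normally the first one to support a claim beyond the primary. Here the only endpoint that both documents call key is absent from the procedure meant to protect such claims. Two endpoints not so labelled in the endpoint sections share the whole 5%. A reader of the endpoint sections would expect a controlled Day 29 result; a reader of 6.11.7 would not. If Day 29 is favourable, the study report must either leave it outside its controlled claims or make a claim that the scheme does not cover.

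The gate raises a second question. A final primary p-value of 0.047, for example, fails protocol 9.7.2 but opens secondary testing under 6.11.7.

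**Working it through.** **1. The plan's own Holm levels.** For two endpoints, Holm gives 0.05/2 = 0.025 and then 0.05, as SAP 6.11.7 states. The first-step total is 0.025 + 0.025 = 0.05. With independent tests the error is 1 − 0.975² = 4.94%. The pair is sound, and its total leaves nothing over for a third endpoint.

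**2. Day 29 claimed at 5% beside the pair.** Take all three secondaries as null and the gate as open.
- Upper bound: 0.025 + 0.025 + 0.05 = 10%.
- Independent tests: 1 − 0.975 × 0.975 × 0.95 = 9.7%.
- Positively correlated tests (trivariate normal, common correlation assumed): 1 − P(|Z1| < 2.241, |Z2| < 2.241, |Z3| < 1.960).

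| Assumed correlation | Family-wise error |
|---|---|
| 0 | 9.7% |
| 0.3 | 9.3% |
| 0.5 | 8.7% |
| 0.7 | 7.7% |
| 0.9 | 6.1% |

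The documents give no correlation, so the table is a range and not an estimate.

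**3. Day 29 placed in the scheme.** A three-endpoint Holm set has levels 0.05/3 = 0.0167, 0.025 and 0.05. With Day 29 tested first at 0.05, the duration pair follows at 0.025 and 0.05 only if Day 29 succeeds. Each arrangement totals 5%.

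**4. The gate.** The information fraction is t = 150/210 = 0.714, and the correlation between looks is √0.714 = 0.845. The total is 1 − P(|Z1| < c1, |Z2| < c2).
- Protocol 9.7.2, 0.0160 then 0.0452 (c1 = 2.409, c2 = 2.003): 5.00%, which reproduces the protocol's design.
- 0.0160 then 0.05 (c2 = 1.960): 5.44%.

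The 5.44% is the chance that the gate opens when the primary is null. If the primary is claimed only at the protocol levels, the additional 0.44 points become an error only when a duration endpoint also rejects falsely. With independent tests that adds about 0.44 × 0.0494 = 0.02 points, giving about 5.02%. Simulation under the global null, with assumed common correlations from 0 to 0.9, gives 5.0-5.1%.

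**5. What the three-endpoint Holm set would cost Day 29.** This uses 70 and 140 subjects and the pooled normal approximation without covariates. The Phase 2 failure rates fell "from 30.0% in the placebo group to 10.5% in the VERU-111 treated group at Day 29".
- Pooled rate: (70 × 0.30 + 140 × 0.105)/210 = 0.17.
- Null SE: √(0.17 × 0.83 × (1/70 + 1/140)) = 0.0550.
- Alternative SE: √(0.30 × 0.70/70 + 0.105 × 0.895/140) = 0.0606.
- Power: Φ((0.195 − z × 0.0550)/0.0606), which is 92.5% at 0.05 and 85.2% at 0.0167.
- With an assumed 15% failure rate on VERU-111, the figures are 71.3% and 56.2%.

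The values at 0.0167 are first-step minima, because Holm tests Day 29 at a higher level if a duration endpoint rejects first. The Phase 2 rates are post hoc, from 39 patients, and the protocol says "The Phase 2 clinical study was hypothesis generating".

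**The case against.** Which secondaries receive formal control is the sponsor's choice. SAP 6.11.7 says its endpoints are selected, names them, and fixes the procedure in a plan whose amendments are headed as made before database lock. The Holm pair does not inflate error. All of this stands. It does not explain why the declared key secondary was left out, and the label conflict remains on the face of the documents.

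A reader might infer that Day 29 has no alpha and can only be reported as nominal. The documents do not support that. SAP 6.11 gives every test a default two-sided 5% level, no passage calls Day 29 nominal, and 6.11.7 says only that all analyses will be presented. The defect is a test level without a place in the multiplicity scheme.

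A reader might also take 5.44% as the trial's overall error. It is that only if the primary is itself claimed at 0.05. The 5% in SAP 6.11 and 6.11.7 can be read as an overall level, with protocol 9.7.2 supplying the criterion for each look. The IDMC plan, which is not among these documents, may say so. That reading softens the gate point, but the literal threshold in 6.11.7 still differs from the protocol's.

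**Conclusion.** The concern holds, and the text should be corrected. The key secondary label is contradicted between five passages and SAP 6.11.7, within the SAP as well as between the two documents. A Day 29 claim is not error-controlled: at 5% beside the Holm pair, family-wise error among the three secondaries is at most 10%, and 6.1-9.7% over the assumed correlations of 0 to 0.9.

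The gate is a smaller, separate conflict. It opens 5.44% of the time under the null instead of 5.00%, but family-wise error stays at about 5.0-5.1% if the primary is claimed only at 0.0160/0.0452. These figures assume normal test statistics, looks at 150 and 210 subjects, and secondaries tested at the look where the gate opens. The main harm is that the two rules can disagree on whether the primary succeeded. The primary analysis under protocol 9.7.2 is unaffected.

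The documents do not show that the key secondary was changed in the light of results, and they do not say whether the interim had taken place by SAP version 5.0 (30-JUN-2022).

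**What to change.** **Day 29.** While still blinded, make the passages agree through SAP 6.11.7, and record the reason in section 9. There are three ways:
- Add Day 29 to a three-endpoint Holm set at 0.0167, 0.025 and 0.05. The first threshold for the duration endpoints falls from 0.025 to 0.0167.
- Test Day 29 first, then apply Holm to the duration pair. The pair is then tested only if Day 29 succeeds.
- Keep the pair and state that Day 29 is not multiplicity-controlled. The declared key secondary then carries no controlled claim.

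The cost is SAP wording, a section 9 entry, a record that the choice was made blind and, for the first two, a change to the shell of Table 14.2.9.1.

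If unblinding has already occurred, leave the prespecified label in place, disclose the discrepancy, and report Day 29 as not multiplicity-controlled. Deleting the label at that stage would itself be a post hoc change.

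**Gate.** Replace p<0.05 in SAP 6.11.7 with the protocol 9.7.2 criteria (two-sided 0.0160 at the interim, 0.0452 at the final analysis), and check the wording against the separate IDMC SAP. The only loss is that a final primary p-value above 0.0452 and below 0.05 no longer opens secondary testing.

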### **9.7.2 Interim Analysis**

An efficacy interim analysis of the primary endpoint, all-cause mortality at Day 60, will be conducted when approximately 71.4% of the subjects (~150 subjects) have completed Day 60, died or withdrawn for other reasons. The first 150 patients randomized into the study will be included in the planned interim analysis. The interim and final analyses will follow an O'Brien-Fleming group sequential design, with a plan of stopping the trial at the interim analysis if the results are statistically significant in favor of VERU-111. The criterion for efficacy at the interim analysis will be a two-sided 0.0160 p-value (a one-sided p-value  $\leq 0.0080$  in favor of VERU-111). If the criterion is not met, the trial will continue, and the final analysis will have a criterion for efficacy of a two-sided p-value  $\leq 0.0452$  (one-sided 0.0226 in favor of VERU-111).

In addition, an estimate of the conditional power that the trial will be positive (statistically significant difference for final analysis) will be provided to the IDMC at regular intervals. If the conditional power is below 0.30 this may suggest termination for futility. However, this would not be a binding rule. Factors other than the conditional power will be considered by the IDMC when weighing the futility of the study as a whole after carefully evaluating various factors, including among others, enrolment rate and safety.

[figure not shown]
The interim analyses will be conducted by an independent statistician and provided to the IDMC. The sponsor will not be unblinded to the data and will only be notified of the recommendation of the IDMC to stop or continue the trial for futility. The sponsor will make such a decision after carefully evaluating various factors, including among others, enrolment rate and safety.

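### SAP 6.11.7 declares the primary endpoint significant at p<0.05, but Protocol 9.7.2 leaves only 0.0452 for the final analysis after the interim look; Protocol 9.7.1 also gives a conflicting interim time

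*SAP*

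**What the plan says.** **Protocol 9.7.2** describes an O'Brien-Fleming design with one interim look, at about 71.4% of subjects. "The first 150 patients randomized into the study will be included in the planned interim analysis", "with a plan of stopping the trial at the interim analysis if the results are statistically significant in favor of VERU-111". The thresholds are explicit: "The criterion for efficacy at the interim analysis will be a two-sided 0.0160 p-value"; otherwise "the final analysis will have a criterion for efficacy of a two-sided p-value" of 0.0452 or less ("one-sided 0.0226 in favor of VERU-111").

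**SAP 6.11.7** starts from the primary p-value. At 0.05 or above, testing stops. "If p-value <0.05 then testing continues to key secondary endpoints", which are days in ICU and days on mechanical ventilation, tested by Holm at 0.025 and then 0.05. The section states: "In this way an overall type 1 (false-positive) error rate of 5% will be maintained", and rules out any key secondary claim "unless the principal analysis of the primary efficacy endpoint using the ITT set is statistically significant at the 5% level".

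**Elsewhere in the SAP.** Section 6.11 sets a two-tailed 5% overall level. Sections 7 and 8 refer interim matters to a separate IDMC plan that is not among the documents. The readable part of Section 9 records that Holm was added, but no change to the protocol's final threshold. The figure 0.0452 does not appear in the SAP.

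**Protocol 9.7.1** places the efficacy interim at about 50% of subjects completing Day 60.

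**The concern.** An efficacy look at 0.0160 uses part of the 5%, so the full 0.05 is no longer available at the final analysis. The protocol accounts for this and the SAP's decision rule does not. A final p of 0.047, for example, would be a failed trial under Protocol 9.7.2. Under SAP 6.11.7 it would be a positive trial with both key secondary endpoints open to claims. With two written rules for the primary mortality test, the choice between them could be made after seeing the p-value.

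The timing conflict matters because the pair 0.0160/0.0452 was derived for a look at 71.4%. The same pair does not hold 5% if the look is taken at 50%.

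**Working it through.** **Inputs.** Interim on 150 of 210 subjects, two-sided 0.0160 (one-sided 0.0080); final two-sided 0.0452 (one-sided 0.0226), all from Protocol 9.7.2. Alternative final level 0.05 from SAP 6.11.7.

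- Information fraction t = 150/210 = 0.714; correlation of the two test statistics under no effect √t = 0.845.
- Critical values: c1 = Φ⁻¹(1 − 0.0080) = 2.409; c2 = Φ⁻¹(1 − 0.0226) = 2.003 (protocol) or Φ⁻¹(1 − 0.025) = 1.960 (SAP).

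**Step 1: reproduce the protocol's boundaries.** The Lan-DeMets O'Brien-Fleming spending function at one-sided α = 0.025 is α(t) = 2{1 − Φ(z₁₋α/₂/√t)}. Here 2.2414/0.8452 = 2.652, so α(t) = 0.0080, or 0.0160 two-sided. Solving for the final level that brings the one-sided total to 0.025 gives 0.02258, or 0.0452 two-sided. Both match. The classic O'Brien-Fleming form gives 0.0174/0.0444 and does not. The protocol names no spending function; this one is inferred from the match.

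**Step 2: overall error under no effect**, with (Z₁, Z₂) bivariate normal:

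- Symmetric: 1 − P(|Z₁| < c1, |Z₂| < c2)
- Interim stop for benefit only, two-sided final: 1 − P(Z₁ < c1, |Z₂| < c2)
- False claim of benefit: 1 − P(Z₁ < c1, Z₂ < c2)

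| Interim / final level | Symmetric | Stop for benefit only | False benefit |
|---|---|---|---|
| 0.0160 / 0.0452, t = 0.714 | 5.00% | 4.76% | 2.50% |
| 0.0160 / 0.05, t = 0.714 | 5.44% | 5.22% | 2.72% |
| 0.0160 / 0.0452, t = 0.50 | 5.38% | 4.95% | 2.69% |

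A simulation of 20 million draws also gave 5.44% for the symmetric case in the second row.

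**Step 3: the disputed window.** The probability that the trial reaches the final analysis with p between 0.0452 and 0.05 in favor of VERU-111 is 2.72% − 2.50% = 0.22% under no effect. It peaks at about 1.6% when the expected final Z is near 2.

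**Step 4: interim timing.** At t = 0.50 the same spending function gives 0.0031/0.0490, so 0.0160/0.0452 belongs to 71.4%. The two sections count slightly differently: 9.7.1 counts completers, 9.7.2 also counts deaths and withdrawals. They would agree only if 105 of the 150 had completed (105/210 = 50%), that is, if 30% had died or withdrawn. The design mortality rates imply (140 × 5% + 70 × 25%)/210 = 11.7% deaths. The 50% may be a leftover, since 150 is half of the 300 subjects planned before the sample size changed; that is inference.

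**Step 5: secondaries under a corrected primary rule.** Take one key secondary with no true effect, tested at one-sided 0.025 at whichever look the primary succeeds, in the worst case over the primary effect. Its error is 2.53%, 2.60%, 2.85% and 3.05% at assumed primary-secondary correlations of 0.3, 0.5, 0.8 and 0.9. The documents give no correlation. Correcting the primary threshold therefore secures 5% for the primary only.

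**The case against.** **The protocol may simply govern.** SAP 6.11.7 is about multiplicity, SAP 6.11 calls 5% the overall level, and the unseen IDMC plan may carry 0.0452. On that reading the primary error is 5.0%. This works for SAP 6.11 but not for step 1 of 6.11.7, which compares the p-value itself with 0.05 and has no cross-reference to the protocol's boundary. SAP version 5.0 (30 June 2022) postdates Protocol version 7.0 (18 March 2022) and cites it, so the two should agree.

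**5.44% is the largest available figure.** The protocol stops at the interim only in favor of VERU-111, which gives 5.22% and 2.72% false benefit. That is correct. 5.44% is the like-for-like comparison with the symmetric 5.00%.

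**The figures are asymptotic.** The SAP's example code uses Firth-penalized logistic regression. Simulating an unadjusted Firth Wald test (100:50, then 140:70), with interim stopping for benefit and 0.05 at the final, gives a two-sided error of about 3.8% to 5.0% for assumed common mortality of 10% to 30%. So 5.4% is not established for the planned test. False claims of benefit are still about 2.7% to 2.9% with 0.05, against 2.5% to 2.7% with 0.0452, depending on how the standard error is formed. This simulation has no covariates or sites.

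**The consequence needs a p-value in a narrow window.** True, and this limits the expected harm. It does not remove the need for a single threshold fixed in advance.

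**Conclusion.** The concern holds. The protocol's boundaries are sound; the defect is that the SAP's decision rule contradicts them and does not deliver the 5% it states. If the SAP text governs, the two-sided error is 5.44% (symmetric) or 5.22% (interim stop for benefit only), with 2.72% false claims of benefit against 2.50%. If the protocol governs, the primary error is 5.0%.

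These figures assume normal-theory test statistics, information proportional to the number of subjects, and a look at 150 of 210. The inflation is modest. The point still must be fixed, because the conflicting rule decides success on the primary mortality endpoint and access to the key secondary claims.

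The 50% against 71.4% conflict is a second, separate inconsistency. The wording about the first 150 randomized subjects favors 71.4%.

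**What to change.** 1. **SAP 6.11.7 and Table 14.2.9.1.** Replace 0.05, both as the primary criterion and as the condition for opening the Holm tests, by the protocol's rule: two-sided p of 0.0160 or less in favor of VERU-111 if the trial stops at the interim, and 0.0452 or less in favor of VERU-111 at the final analysis.
2. **Protocol 9.7.1.** Change 50% to 71.4% (first 150 randomized). Alternatively, name the spending function and state that boundaries are recomputed at the actual information fraction.
3. **The 5% statement in SAP 6.11.7.** Either limit it to the primary endpoint, or test the secondaries at the same spending function's levels at the look where the trial stops. The Holm step at 0.025 then becomes about 0.0062 (interim) or 0.0231 (final), and the step at 0.05 becomes 0.0160 or 0.0452.

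Items 1 and 2 are wording changes, and item 1 adopts thresholds the protocol already states. Item 3 costs nothing if the statement is limited to the primary. Otherwise it costs some power for the two secondaries, mostly if the trial stops at the interim. All should be settled before unblinding.
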